Potential participants' mental capacity is anticipated as ranging from able to give informed consent to lacking capacity to give informed consent. Incorporating different consent procedures is used in research studies on end of life care ⁴⁹⁻⁵¹. We will use consent procedures that are aligned to an individual's level of capacity, incorporating varying levels of capacity and anticipating that some participants may lose capacity during the study. This intends to enable individuals with varying levels of capacity to decide for themselves if they wish to participate, and to enable participation by adults lacking capacity. A witnessed consent will be included in the informed consent, and in the personal consultee declaration.

Consent in the moment for participants with impaired capacity

For adults with impaired capacity, who are able to understand, retain and weigh-up information in the moment, a procedure of consent in the moment is used with ongoing consent whereby informed consent to participate is verbally reaffirmed prior to each data collection point ⁵³. The approach of consent in the moment was developed and used in studies involving adults with dementia and/or cognitive impairment ^{53,54}. If a participant's capacity declines and they are no longer able to give informed consent in the moment, the researchers follow the procedure for adults lacking capacity detailed below.

Adults lacking capacity

When an adult lacks capacity advice will be sought from a personal consultee about the person's participation in the study. If no personal consultee is identified, or does not respond to requests for advice, a nominated consultee will be asked to review and advise about participation. Participation is low risk. It will involve accessing the person's patient health records in the community hospital, the consultee (or other family member, close friend or staff when no family/friend) completing the study questionnaires on the person's behalf, and non-participant observation of clinical meetings about the person e.g. the Welcome meeting on admission with the informed consent of those participating in the meeting i.e. the family member, clinical staff.

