For adults lacking capacity the questionnaires will be completed by a proxy informant. The proxy informant will be the personal consultee, or another family member (for example the patient's son or daughter) or a close friend. If no family/friend are available the research questionnaire will be completed by a member of the community hospital staff who knows the person, and the post-discharge questionnaire completed by, for example, care home staff. The proxy informant will self-complete the questionnaires on hard-copies either in the hospital or completed at home. Questionnaires will be returned by post to the project team at King's College London. We will make available an online questionnaire if this format is preferred. The proxy informant will be assisted to complete the questionnaires by telephone video call, during the COVID-19 pandemic or face-to-face after the pandemic as required by the research team or research nurses. Only remote interviews will be conducted with consultees during the pandemic. The research team will use two reminders with informants to complete the respective questionnaire. This will include a telephone call two weeks after giving or posting the respective questionnaire (or email or letter will be used if no phone number is available or calls are unanswered). If no response after 4 weeks we will post or email a reminder letter and enclose the respective questionnaire booklet, reply slip and Free post envelope. The questionnaires will be checked for completeness by the researchers/research nurse, and a follow-up telephone call made to the participant to check accuracy if data is missing or to clarify a response when unclear.

Each patient or proxy informant (e.g. the personal consultee or other family member) will receive a thank you card and £5 voucher after completing the data collection during the admission. The card and voucher will be given to the person or posted to their address. The card will thank the person for participating in the study, state that their views are important and that we will ask them to complete a further questionnaire after they (or the person cared for) is discharged. We will post a further thank you card once data collection is completed, thanking the person for participating. The thank you cards will include the research team's contact details and indicate for the person to contact the team if they have any queries or questions about the study.

Distress protocol

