Feasibility of the research methods

Sample size

The patient total sample size is 40 patients across the two community hospitals, with sample 1 comprising 20 patients and sample 2 comprising 20 patients. We will review the recruitment rate for sample 1, if recruitment is feasible within the timeframe, we will increase the sample 2 size to n=30. The sample size is informed by understanding that feasibility studies should include a minimum of 30 patients, and account for attrition. Attrition is calculated at ~30% as a typical rate for a study in palliative care.⁴⁷ A sample of 40 is considered sufficient for a feasibility study to explore the feasibility of recruitment to the study and the parameters to inform the sample size calculation in a future pilot trial.⁶³ We will recruit a maximum of 12 patients lacking capacity to assess the feasibility of the consultee process to advise on participation, and proxy reporting of research data. Patients lacking capacity will be recruited in sample 1 (pre-SPACE) and sample 2 (after-SPACE embedded). We will review our consultee process in the sample 1 recruitment to identify potential modifiers to enable participation.

Main candidate outcome

We will explore the feasibility and acceptability of a proposed candidate main outcome comprising 'Patient/family anxiety and communication subscale' of the Integrated Palliative Outcome Scale (I-POS)⁶⁴⁻⁶⁶ ⁶⁷ ⁴⁹. Anxiety and communication are common distressing concerns for patients on admission to hospital and their families. These concerns are often exacerbated when clinical presentation is uncertain. The Patient/Family anxiety and communication subscale comprises 7 items of the I-POS⁶⁶. The items concern information, practical matters, shared feelings, at peace, patient anxiety, family anxiety, and patient depression. Items are scored from 0 (best) to 4 (worst) and can be completed by the patient or a proxy (e.g. staff or family member) for adults lacking capacity. The I-POS is the latest refinement and improvement of the well validated and widely used Palliative care Outcome Scale (POS) developed and tested in palliative care⁶⁶. The POS has been used in community and hospital settings, including in nursing homes (UK and the Netherlands), and in many different conditions including dementia,⁶⁷ heart failure⁶⁸, COPD,⁶⁹ cancer, neurological conditions,⁷⁰ and multiple comorbidity⁶⁷.

Secondary candidate outcomes

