- Palliative concerns not included in the patient/family subscale (I-POS)⁶⁶
- Patient Reported Experience Measure (PREM) from the NHS National Benchmarking of Community hospitals (2018) https://members.nhsbenchmarking.nhs.uk/dashboard/2
 - o I had confidence and trust in the staff treating or supporting me
 - o Overall, I felt I was treated with respect and dignity from this service
- Physical disability (Modified Barthel Index)⁷¹ (during admission timepoints)
- Function (Australian Karnofsky Index for palliative care)⁷² (during admission timepoints)
- Frailty (Fried's Phenotype of Frailty¹) (during admission timepoints). We will review the suitability of Fried's frailty scale for adults lacking capacity in our initially piloting of the questionnaires. The Fried measure includes physical assessment of hand strength, and for people able to walk, a timed 4 meter walk speed. We will review level of missing and feedback from the data collectors. If unsuitable we will remove Fried and replace with *FRAIL* ⁷³. FRAIL score is similar to Fried. FRAIL is very brief (2 minutes) measure of frailty comprising 5 items assessing fatigue, resistance, ambulation, illness and loss of weight. Each item is assessed using a different response option, but no physical measure of sarcopenia
- Survival at 6 months by review of NHS site electronic patient records

Process outcomes

- Community hospital length of stay
- Review and audit of patient records using a data sheet to record completion of the SPACE documents and decision-making³³ e.g. staff involved, completed proxy/selfreport, communication multi-disciplinary teams and with patients and families. Collect completed and de-identified copies of the SPACE documents, including IPOS-Dem, the adapted-PACE and the Anticipatory Care Plan.

Economic evaluation

Comprises EQ-5D⁷⁴ as a quality of life measure recommended in cost-effectiveness analyses and the Client Service Receipt Inventory (CSRI) to record formal inpatient service use, medication and informal care.^{75, 76} The economic data will be recorded in the admission questionnaire reporting the preceding 12 weeks, and repeated in the discharge questionnaire (28-42 days after discharge).

Embedded qualitative study

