The SPACE documents will be completed by staff in the respective community hospital (nurses, allied health professionals, medical doctors and health care assistants in a supportive role). The documents are intended to be incorporated in the individual patient document (IPD) (paper or electronic) used in clinical practice in the study site. How well (or not) the SPACE documents are used will be assessed in the study training phase (before SPACE embedded in clinical care) by auditing patient records in the community hospital, and non-participant observation of specific clinical activities, e.g. multi-disciplinary team meetings (see table 3). The findings will inform modifications to support use in the assessment phase (After SPACE embedded in clinical care).

Using the documents in clinical care will be supported by a manual on the SPACE documents detailing how to use, nursing/clinical leads (e.g. Modern Matron, ward manager and ward sister) and a designated champion(s) for SPACE in each participating community hospital. These individuals will provide ongoing support e.g. peer teaching, role modelling. They will draw on the expertise from the ward based Advanced Nurse Practitioner and Geriatrician/ Specialist doctor, and trust wide specialty leads for end of life care and dementia care. The process of using the SPACE documents is from admission to discharge for all patients in the participating community hospitals. The process of using the documents will consist of four key elements:

- 1. Ensure a comprehensive assessment on admission to identify priorities for the patient/family including physical, psychosocial and spiritual concerns; and potential for rehabilitation. Identify and agree:
 - a. the goals of care, including rehabilitation goals and patient priorities
 - b. planned treatment and care, including discharge date and place of discharge
 - c. manner and timing of monitoring and evaluation
- 2. Arrangements to discuss and agree care and/or proposed changes with the patient/family
- 3. Review prior to discharge by repeating the assessment tools (IPOS-Dem and CFS) to give information on discharge on performance status (function), patient priorities and symptoms and concerns (deficits).

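### Ward staff who deliver SPACE may answer the research questionnaires, including two items on their own care, and the ceiling of 12 patients lacking capacity is not divided between the before and after samples

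*Protocol*

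**What the plan says.** Under Data collection methods, the informant for an adult lacking capacity is the personal consultee, another relative or a close friend. Failing these: "If no family/friend are available the research questionnaire will be completed by a member of the community hospital staff who knows the person". The same sentence goes on to have "the post-discharge questionnaire completed by, for example, care home staff". The consent section (Adults lacking capacity) gives the same fallback: "the consultee (or other family member, close friend or staff when no family/friend) completing the study questionnaires on the person's behalf". The Main candidate outcome section accepts staff as I-POS proxies.

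Under Frequency and duration of SPACE: "The SPACE documents will be completed by staff in the respective community hospital", and "The process of using the SPACE documents is from admission to discharge for all patients in the participating community hospitals". The staff listed there are nurses, allied health professionals, doctors and health care assistants.

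Secondary candidate outcomes lists two patient-experience items. One is "I had confidence and trust in the staff treating or supporting me"; the other concerns respect and dignity from the service. Neither carries an exemption for a staff informant.

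Under Sample size: "We will recruit a maximum of 12 patients lacking capacity to assess the feasibility of the consultee process", and proxy reporting of research data. The next sentence says that such patients will be recruited in both samples, but gives no number for either. Samples are 20 and 20, and the second may rise to 30.

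**The concern.** Two things are at stake. The first is what the experience items mean. If a ward nurse answers for a patient whether that patient trusted the ward staff, the answer is a staff self-assessment filed as patient experience.

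The second is comparability. Quantitative analysis compares sample 1 with sample 2, looks at degree of change, and takes mean and variance estimates forward to the next trial. If patient, family and staff ratings are mixed in different proportions in the two samples, part of any difference may reflect who answered. A change of informant between hospital and home has the same effect within a patient.

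**Working it through.** **Who rates.** The informant rule asks only that the staff member knows the patient. It does not ask that this person stand outside the patient's care. By contrast, the consent section bars a nominated consultee from involvement in direct care. Independence is therefore required of the person who advises on participation, but not of the person who supplies the outcome data.

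**What is rated.** The experience items have no timepoint attached, whereas the Barthel, Karnofsky and frailty measures are marked for admission only. The Plain English summary says that the questionnaires, given twice in hospital and once after discharge, ask about experiences of care. I read this as placing the two items in the in-hospital questionnaire. The only self/proxy record that the protocol names is in the audit of SPACE documents (Process outcomes), not on the research questionnaires.

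**Share lacking capacity.** The figure of 12 is set, not derived, so there is nothing to reproduce. It is 12/40 = 30%, or 12/50 = 24% if sample 2 rises to 30. Let a and b be the numbers lacking capacity in samples 1 and 2, with a + b = 12 and each at least 1. The gap is b/n2 − a/n1. The shift in the before/after contrast is the gap times the proxy-versus-self offset. The documents give no offset, so I assume 0.25 to 0.75 SD.

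| n1+n2 | a / b | Shares | Gap (points) | Size of shift (SD) |
|---|---|---|---|---|
| 20+20 | 6 / 6 | 30% v 30% | 0 | 0 |
| 20+20 | 8 / 4 | 40% v 20% | −20 | 0.05 to 0.15 |
| 20+20 | 11 / 1 | 55% v 5% | −50 | 0.13 to 0.38 |
| 20+30 | 5 / 7 | 25% v 23% | −2 | 0.00 to 0.01 |
| 20+30 | 6 / 6 | 30% v 20% | −10 | 0.03 to 0.08 |
| 20+30 | 8 / 4 | 40% v 13% | −27 | 0.07 to 0.20 |
| 20+30 | 11 / 1 | 55% v 3% | −52 | 0.13 to 0.39 |

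The 8 / 4 rows apply the site's 40% rate of dementia or cognitive impairment to sample 1 (0.40 × 20 = 8). That is an upper value, since impairment is not the same as lack of capacity.

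**Chance alone.** If 12 such patients fall at random among all recruits, a is hypergeometric: P(a = x) = C(n1, x) C(n2, 12 − x) / C(n1 + n2, 12). A gap of at least 20 points means x ≤ 4 or x ≥ 8 with 20+20, which has probability 0.30. With 20+30 it means x ≤ 2 or x ≥ 8, which has probability 0.09.

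**Yardstick.** The standard error of the difference is √(1/n1 + 1/n2) SD: 0.32 SD with 20+20 and 0.29 SD with 20+30.

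**The case against.** The case against is substantial. This is a feasibility study, testing proxy reporting is a stated purpose, and the before/after comparison is exploratory. Staff are a last resort, and how often they will be needed is not given. The table counts all proxies, so it does not measure the effect of staff ratings specifically. Summaries by informant are usually left to an analysis plan, and the protocol refers to one. Dropping staff-rated records would remove patients without family, although the section on the Mental Capacity Act includes people with impaired capacity precisely to limit sampling bias. All of this stands. It lowers the weight of the point and shapes the remedy. It does not reach the informant rule, the experience items without exemption or the undivided ceiling, which the protocol itself fixes. Analysis afterwards cannot rebalance recruitment.

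A reader might infer more than the text supports:

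- That the ceiling permits 12 v 0. It does not: both samples are to include such patients, so 11 v 1 is the extreme.
- That sample 1 raters have had no contact with SPACE. Sample 1 is collected during the training phase, when staff are trained and begin using the documents (Table 3). Familiarity differs in degree.
- That staff ratings favour SPACE. No direction is documented. I-POS runs from 0 (best) to 4 (worst), so self-flattering ratings would be lower, and with more proxies in sample 1 they would count against SPACE. Training might equally lead staff to notice more concerns.

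**Conclusion.** The point holds, with moderate weight. The firm part needs no arithmetic: the protocol lets staff of the hospital delivering SPACE answer two items about their own service on the patient's behalf, and requires no uninvolved informant. It also lets the informant change after discharge.

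The undivided ceiling is a real but smaller weakness. A 20-point gap in proxy share is plausible by chance with 20+20. Its effect, 0.05 to 0.15 SD, is well below the standard error of 0.32 SD. Only near the 11 v 1 extreme does the shift approach or pass that standard error, and then only at the top of the assumed range. These sizes rest on an assumed offset, on a full 12 such patients, and on treating family and staff proxies alike. Patients who lose capacity after enrolment would add proxy data beyond the 12.

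**What to change.** 1. Do not collect the two experience items from staff informants.
2. Record informant type (patient, family or friend, ward staff, care home staff) on every research questionnaire. Show the main-outcome mean, SD and before/after contrast with and without staff-rated I-POS, so that patients without family are not simply dropped.
3. Divide the ceiling in proportion to sample size: 6/6 for 20+20, about 5/7 for 20+30. The size of sample 2 is decided after reviewing sample 1, so holding sample 1 to 5 keeps both options open: 5/5 gives 25% v 25%, and 5/7 gives 25% v 23%. A ceiling limits imbalance but does not guarantee equal shares, and it does not equalise the family/staff mix among proxies. Item 2 is needed for that.
4. Flag change scores where the informant differed between timepoints.

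The cost is protocol and form wording, a few missing experience items, and slightly less flexible recruitment of patients lacking capacity. Staff-completed questionnaires still count towards the feasibility of proxy reporting.

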The incorporation of tools and measures in clinical practice are often impeded by clinicians' limited expertise and familiarity⁸⁴. Our development work informed the processes of using the SPACE documents (workstreams 1 and 3). We also drew on national and international work on embedding the use of outcome measures in clinical practice in palliative care. This included studies undertaken in the Cicely Saunders Institute (CSI), on the knowledge mobilisation of outcome measures in palliative care in the UK (http://www.csi.kcl.ac.uk/oacc.html) and in Australia⁸⁶, systematic reviews on implementation in clinical practice,^{90, 91} and resources on using outcome measures in clinical practice^{82, 92} and specifically the POS family of measures, for example the Clinical Decision Support tool⁹³, and web resources http://pos-pal.org/.

Table 3 The phases and activities to use the SPACE documents

Activity	Actions required	
Training phase (before): focusing on the processes and feasibility of using in clinic practice, auditing clinical records and amending processes accordingly.		
Setup SPACE in two hospitals. Sequential design implement, audit, learn and refine hospital 1, inform hospital 2	Sequential working with hospitals. Commence 1st hospital setup, auditing, learning and refining. Then commence 2nd hospitals. 1st hospital setup period over a month working with staff to refine processes of embedding in routine care practices. 2nd hospital commence implementation process refined from hospital 1. Work with staff in hospital 2 over a month to embed processes in routine practice.	
Face-to-face training (conducted over a month in each site)	Face-to-face training approx. 2 hours in each site led by [name] (project lead), and site lead/champion working with the education lead. A training manual details specific documentation and processes for use. Training repeated if needed to enable participation of all clinical ward staff (e.g. nurses, AHPs, HCA, social worker, doctor). The training will focus on the introduction of SPACE, the specific documentation and incorporation in the individual patient-centred plan. The training is developed from the review of the evidence on managing clinical uncertainty (WS1) and consultation with clinical staff and patients/families on priorities on key processes (assessment, communication and continuity of care) (WS3).	

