- 1. Descriptive analysis on the number of patients screened for eligibility and the proportion of eligible patients recruited and reasons for decline, and differences between participants and non-participants e.g. age, gender
- 2. Descriptive analysis on completion of the SPACE documents from the patient record data extraction on when completed, proportion of missing data, and use over time e.g. IPOS-Dem to review and evaluate outcomes of care.
- 3. Examining the candidate main outcome of *patient/family anxiety and communication subscale* and secondary outcomes. We will examine missing data and evaluate the impact on results. We will explore the before (sample 1) and after (sample 2) measures and degree of change in the candidate main and secondary outcomes using non-parametric test for categorical data (e.g. Chi-Square) or parametric tests for continuous variables (e.g. T-Test).
- 4. Examine reasonable mean and variance estimates of the main outcome to inform the sample size calculation in a future pilot/full trial and estimates of inter-correlation co-efficient by examining variation between hospitals e.g. age, length of stay.
- 5. The data analysis in the economic evaluation will explore procedures to inform the economic evaluation in a pilot/full RCT. Economic evaluation is an emergent area in studies with patients with advanced progressive conditions and uncertainty surrounds best practice ⁷⁶.

Qualitative analysis

We will undertake a full coding of focus group and interview transcripts, non-participant observations and fieldnotes to identify themes using constant comparative approach⁹⁴ in NViVo⁹⁵. Data analysis will explore the range of experiences of staff using the documents in clinical care exploring feasibility and acceptability, solutions and barriers to enhance use, and potential benefit for patients and families. Quality appraisal will use procedures to ensure systematic attention to analysis and reporting e.g. analysis review meetings.

Ethics and regulatory approvals

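### Sample sizes are set in total across two hospitals with no split per hospital, so a change in hospital mix could enter the exploratory before-after estimate

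*Protocol*

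**What the plan says.** The Sample size section of the protocol gives the numbers as "40 patients across the two community hospitals, with sample 1 comprising 20 patients and sample 2 comprising 20 patients". It adds that, after the sample 1 recruitment rate has been reviewed, "if recruitment is feasible within the timeframe, we will increase the sample 2 size to n=30". No target, minimum or cap per hospital appears anywhere, and the hospital that would supply the extra 10 patients is not named.

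The section on data collection timepoints gives each hospital its own windows: 2-3 months for sample 1 and two months for sample 2. Both samples are therefore meant to draw on both hospitals.

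Table 3 introduces SPACE one hospital at a time: "Sequential design implement, audit, learn and refine hospital 1, inform hospital 2".

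Item 3 of the quantitative analysis states: "We will explore the before (sample 1) and after (sample 2) measures and degree of change", for the candidate main and secondary outcomes, with chi-square and t-tests as examples. It does not mention hospital. Item 4 looks at variation between hospitals, but only to inform a future trial.

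**The concern.** The before and after groups are different patients, and the only link between them is that they come from the same two hospitals. That link holds for the comparison only if the hospitals make up the same proportion of each group. The protocol fixes the totals and leaves the proportions to whatever recruitment delivers.

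If one hospital supplies more of sample 1 and the other more of sample 2, any standing difference between them in patients or staffing shows up as a before-after difference. What is at stake is the exploratory estimate of change in the candidate main and secondary outcomes. The objectives on recruitment, process and missing data do not depend on that contrast.

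**Working it through.** **Inputs.** From the protocol: samples of 20 and 20, with sample 2 possibly 30; windows of 2-3 months (sample 1) and two months (sample 2) in each hospital; attrition of about 30%. Not in the protocol: the difference between hospitals, called D here. I assume 0.5 SD and show 0.2 and 0.8 SD as a range.

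**The plan's own figure.** 20 + 20 = 40, as stated. The justification cites a minimum of 30 and attrition of about 30%: 30 x 1.3 = 39, close to 40, and 40 x 0.7 = 28 completers. The present point does not depend on how 40 was reached.

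**Formula.** Let p1 and p2 be hospital 1's shares of samples 1 and 2. With no effect of SPACE, the expected difference between the samples is |p1 - p2| x D. The standard error of the contrast in SD units is sqrt(1/n1 + 1/n2): sqrt(1/20 + 1/20) = 0.316 for 20 v 20, and sqrt(1/20 + 1/30) = 0.289 for 20 v 30.

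**Splits that the text permits** (hospital 1/hospital 2):

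| Sample 1 v sample 2 | Change in share | D = 0.2 | D = 0.5 | D = 0.8 |
|---|---|---|---|---|
| 10/10 v 10/10 | 0 | 0 | 0 | 0 |
| 15/5 v 15/5 | 0 | 0 | 0 | 0 |
| 12/8 v 8/12 | 0.60 - 0.40 = 0.20 | 0.04 | 0.10 | 0.16 |
| 10/10 v 10/20 | 0.50 - 0.33 = 0.17 | 0.03 | 0.08 | 0.13 |
| 15/5 v 5/15 | 0.75 - 0.25 = 0.50 | 0.10 | 0.25 | 0.40 |

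The second row shows that imbalance as such is harmless; only a change in mix matters. The fourth row shows that a balanced sample 1 is not enough if all the extra patients come from one hospital. In the extreme last row, at D = 0.5, a two-sided test at a nominal 5% level would reject about 12.4% of the time with no effect of SPACE (normal approximation; the protocol sets no level).

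**Does the staggered start cause a shift?** Filling 20 places from two hospitals over 2-3 months implies 20/(2 x 3) = 3.3 to 20/(2 x 2) = 5 patients a month per hospital. Assume equal rates r and a one-month lead, so that r x t + r x (t - 1) = 20.

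- At r = 5, t = 2.5 and the split is 12.5 : 7.5, a hospital 1 share of 62.5%.
- At r = 3.3, t = 3.5 and the split is about 11.7 : 8.3, a share of about 58%.

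The same lead applies in the after phase. Sample 2 over two months implies 5 a month and again 62.5%. The change in share is then 0 to about 4 percentage points, or 0 to 0.02 SD at D = 0.5. If each hospital simply runs its full window at an equal rate, the split is 10 : 10.

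**Effect of the fix on precision.** With 10 per hospital in each sample, each within-hospital difference has standard error sqrt(1/10 + 1/10) = 0.447. The average of the two has sqrt(0.447² + 0.447²)/2 = 0.316, the same as the pooled contrast. After 30% attrition each cell holds about 10 x 0.7 = 7 completers.

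**The case against.** The best defence is that the protocol already gives each hospital its own before and after window, so both samples should contain both hospitals and complete confounding of hospital with phase is unlikely. That stands. What it does not do is fix the shares: the windows are defined by time, differ in length between the samples and sit under a total cap, and the optional enlargement has no rule by hospital.

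A second defence is that no objective estimates effectiveness and item 3 is exploratory. That also stands, and it limits the weight of the point. Even the extreme split gives a shift below the standard error.

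A third is that stratification by hospital may be in an analysis plan not shown here; the data-sharing section refers to a pre-agreed one. That is possible, but recruitment numbers per hospital belong in the protocol, and analysis cannot recover a nearly empty combination of hospital and phase.

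A fourth is that a quota would cut short the observation of recruitment. The criterion is three in ten of eligible patients approached. Being a proportion, it is not undermined by a quota.

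Three stronger readings are tempting, and the documents do not support them:

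- A reader might infer from "Commence 1st hospital setup, auditing, learning and refining. Then commence 2nd hospitals" that the sequence itself distorts the comparison. It does not: hospital 1 leads in both phases, and at the recruitment rate that the plan implies the shares barely move. For the same reason, a hospital 1 share of 75% is an extreme, not an expectation.
- A reader might infer from "2nd hospital commence implementation process refined from hospital 1" that the hospitals use different versions of SPACE during sample 2. That sentence concerns how SPACE is introduced in the training phase. Nothing says that the documents or their use differ by hospital in the assessment phase.
- A reader might extend the harm to length of stay. The protocol lists that as a process outcome, and item 3 compares only the candidate main and secondary outcomes.

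**Conclusion.** The point holds as a minor one. The protocol fixes totals and not hospital shares, leaves the source of 10 possible extra sample 2 patients open, and describes a contrast that takes no account of hospital. A change in mix, arising from uneven recruitment or an uneven enlargement, would pass directly into the exploratory estimate of change.

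At an assumed hospital difference of 0.5 SD, moderate changes in mix give about 0.08 to 0.10 SD and the extreme one 0.25 SD, against a standard error of about 0.3 SD. If the shares stay the same, the effect is zero. These sizes rest wholly on the assumed difference and on splits that the text allows but does not predict.

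**What to change.** In the Sample size section, set the same hospital split in both samples: a target of 10 patients per hospital in each, and 15 per hospital in sample 2 if it is raised to 30. At recruitment this makes the mix effect zero whatever the hospital difference, with totals unchanged at 40 or 50.

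In item 3 of the quantitative analysis, state that the before-after difference is estimated stratified by hospital, as the average of the two within-hospital differences. This also covers uneven attrition. Show the within-hospital results descriptively only, since about 7 completers per cell are expected.

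The cost is one sentence on recruitment and one on analysis, with no extra patients and no loss of precision. The downside is that the slower hospital may take longer to reach its number, which could stretch its window.
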